7.3.3 Expert panel – modified Delphi process

We will select a panel of international experts from relevant publications identified in our systematic review. The panel will undertake a modified Delphi process to identify a list of potential risk factors for AFACS.

Stage 1 of the Delphi process will involve panel members suggesting all risk factors they feel may be predictive of AFACS. These candidate variables will be collated and passed back to the panel in Stage 2. The panel will review all variables generated during stage 1, selecting those they judge to be most important. Variables meeting a consensus agreement of 60% will be accepted (56,57); those <20% will be rejected. In stage 3, variables with 20-60% agreement will be presented to the panel, along with their respective percentage agreement, for a final round of voting. Variables that achieve at least 60% agreement will be added to those previously accepted in Stage 2 to form the final list of candidate variables from the Delphi process.

7.3.4 Machine learning methods – exploring combinations of risk factors in CALIBER and PRD

We will combine all candidate variables identified from the systematic review, CALIBER analysis and Delphi into a combined "long-list". Any variables missing from the PRD (to be used for model development) will be extracted from the electronic patient record. We will then apply machine learning methods (see Section 10) to the CALIBER and PRD data sets to derive combinations of risk factors (i.e. interactions) that should be considered for inclusion in model development.

7.3.5 Expert panel – consolidating risk factors to be used in model development

At their final meeting, the expert panel will review the final long-list of candidate variables (and their combinations). Any variables judged to be redundant or likely to represent spurious correlations will be removed.

7.4 Model development – PARADISE-1 and PARADISE-2

Using the PRD data set, we will develop two prognostic models (PARADISE-1 and PARADISE-2) to predict AFACS using the long-list of candidate variables identified above.

PARADISE-1 will only use patient data collected in pre-operative period (i.e. in the pre-operative assessment clinic or on admission for surgery).

PARADISE-2 will include additional data available on arrival in the post-operative care unit.

In developing both models, we will consider standard statistical approaches (e.g. logistic regression) and machine learning methods (e.g. random forests, deep neural networks). Model performance will be assessed using standard metrics (e.g. calibration, discrimination) and for optimism using internal validation. Further details are given in Section 10.

7.5 Model validation – PARADISE-1 and PARADISE-2

Evaluating the prediction models using the same data used to develop them will lead to optimistic estimations of performance. Therefore, we will externally validate (assessing calibration and discrimination) both models using:

- Retrospective data from one US hospital (Brigham)
- Externally validate models on prospective data from UK NHS Trusts
- Externally validate models on prospective data from a clinical trial data set (TIGHT-K)

Retrospective external validation on the Brigham data set will comprise 3000 individuals (≈900 AFACS events, much larger than the minimum recommended sample size of 100 events (58).

Prospective external validation will be performed on four cohorts. Data collected within clinical trials and "real-world" data from patients receiving routine clinical care offer different strengths and weaknesses when validating a prediction models (59). We will therefore undertake prospective external validations in both trial patients (using data from the Tight K study CS/18/3/34063 and PROPHESY studies (BHF pilot PG/17/82/33368) and in a prospective cohort of ≈6000 patients developed from enhanced routine data collection at NHS trusts. Data from the Tight K and PROPHESY studies bring the advantages of multiple centres and study-grade data collection, but in relatively small numbers – we estimate between one half and two thirds of the total intended recruitment will be available for model validation, totalling over 1000 trial patients. Data from the NHS Trusts provide a large "real-world" prospective validation, but will likely contain more missing data (60).

Ethical approvals for enhanced data collection will be obtained prior to analysis.

As part of the external validation, we will assess the need for recalibration and use decision curve analysis to identify appropriate cut-offs for risk stratification (61). Further details are given in Section 10.

We will compare our prediction models to those identified in the systematic review. These will include the CHA₂DS₂VASc score (originally designed to predict stroke in AF) which has also been used to predict AFACS (62,63)

8 PARTICIPANT IDENTIFICATION

8.1 Study Participants

The study will include all adult patients who underwent or are about to undergo cardiac surgery in any of the study databases or clinical trial data sets.

8.2 Inclusion Criteria

Clinical Research Protocol Template version 15.0 CONFIDENTIAL © Copyright: The University of Oxford and Oxford University Hospitals NHS Foundation Trust 2019 Page 17 of 34

- Patients 18 years or over
- Admitted to hospital for any cardiac surgery

8.3 Exclusion Criteria

• Patients who have requested that their data not be used for research (e.g. NHS Opt-out, see Section 9.3.1)

9 PROTOCOL PROCEDURES

9.1 Recruitment

Participants will be recruited from the study databases and trial data sets, as described in section 7.2.

9.2 Screening and Eligibility Assessment

9.3 Informed Consent

Existing ethical approvals are in place for the CALIBER (UK), PRD (US) and Brigham (US) databases.

For the remaining data sets (including the TIGHT-K trial) used for external validation, we will apply for Health Research Approval (HRA), under advice from the Research Ethics Committee and the Confidentiality Advisory Group (CAG) to allow access to confidential medical records without specific written consent (Section 251 support).

9.3.1 Opt-out

For data sets that include UK participants, the study will fully support and implement the NHS National Opt-out. We will use our link to NHS Digital asking them to inform us which patients have opted out and that will be a continuous process from enrolment until the study ends. Records that are already flagged within each site as meeting the Opt-out will not be extracted.

If we are informed by NHS Digital of patients completing the Opt-out after data extraction, these data will be purged and future records relating to these patients will not be extracted.

We will also purge records from the study (in the same manner) if patients contact the study team directly.

We will clearly display on the website links to register for the opt-out, as well as contact details for the study team.

9.4 Enrolment

This is a non-randomised observational study. Enrolment of participants will occur through their data being present within the participating databases or prior enrolment into the Tight-K study.

9.5 Description of study intervention(s), comparators and study procedures (clinical)

This is a non-interventional study.

9.6 Baseline Assessments

Not applicable

9.7 Subsequent Visits

Not applicable

9.8 Sample Handling

No additional samples will be taken during this observational study.

9.9 Early Discontinuation/Withdrawal of Participants

This is an observational study. Participants can request their data to be deleted at any time in accordance with GDPR and the study privacy policy.

9.10 Definition of End of Study

The end of the study will be when all prospective data sets have been collected and used to externally validate both prediction models (PARADISE-1, PARADISE-2).

10 SAFETY REPORTING

This is an observational study, so safety reporting is not applicable.

11 STATISTICS AND ANALYSIS

11.1 Statistical Analysis Plan (SAP)

The statistical aspects of the study are summarised here, with details fully described in a statistical analysis plan that will be available before any analysis takes place.

11.2 Description of the Statistical Methods

11.2.1 Model development

In the PRD, we anticipate that around one third of patients will experience AFACS (10,000 events), so the issue of overfitting is negligible. Using logistic regression, we will select variables using least angle selection and shrinkage operator (LASSO) penalties (64). Continuous predictors exhibiting a nonlinear relationship with AFACS will be modelled using fractional polynomials.

Heterogeneity in model performance will be explored over different hospitals using internal-external cross-validation (65). We will overcome challenges arising from the use of treatments during the study in two ways: Treatments at or before baseline will be handled by including treatments as predictors (66). The impact of any treatments on the absolute risk of AFACS during follow-up will be investigated using inverse probability weighting (59).

In parallel we will investigate machine learning (ML) approaches to developing a prediction model, including methods such as random forests, deep neural networks, and Bayesian Gaussian processes. Such models allow consideration of interactions between available variables providing "latent variables" (complex, non-linear transformations of the original input variables) that may improve prediction performance over the non-transformed input variables. We will prioritise principled, probabilistic methods that permit the incorporation of prior clinical knowledge, such that results are "interpretable", avoiding the "black box" nature of much ML-oriented research in this area (67,68). We will exploit the ability of the complementary modern ML fields of (i) Bayesian non-parametric modelling (which provides a principled means of coping with artefact and measurement noise in the clinical data) and (ii) deep learning, which permits the fusion of large quantities of (potentially time-varying) clinical variables. These models include components ("attention mechanisms") that allow the resulting risk estimations to be interpretable for clinicians. Importantly, these models permit the model to quantify its uncertainty in its score prediction – whereas conventional medical statistical methods always output a score, ML models have the opportunity to quantity probabilistically the certainty with which a score is produced; this offers advantages in applications in which classes are substantially overlapped, as often occurs in complex, real-world clinical problems, where there is imperfect class separation. Accuracy of such models can often be substantially improved by permitting a model not to make a classification if the score is highly uncertain; such approaches are used in many application areas of critical systems to improve acceptability with users.

Additionally, we will investigate the joint construction of phenotypical clustering models (which identify reproducible phenotypes in the physiological data) with predictive models specific to each phenotypical group – this novel approach constructs an ensemble of predictive models that are phenotype-specific, thereby improving predictive accuracy with respect to a single "one-size-fits-all" generic algorithm applied to the entire population.

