3 SYNOPSIS

Study Title	Predicting AF after Cardiac Surgery - the PARADISE Score. A Clinical Prediction Rule for Post-operative Atrial Fibrillation in Patients Undergoing Cardiac Surgery			
Internal ref. no. / short title	PARADISE			
Study registration	ClinicalTrials.gov: NCT05255	5224		
Sponsor	University of Oxford Clinical Trials & Research Go [name], United Kingdom	overnance,		
Funder	NIHR National Institute of H Programme (NIHR131227)	ealth Research, Health Technol	ogy Assessment	
Study Design	Longitudinal cohort study			
Study Participants	Patients who have undergo	ne cardiac surgery		
Sample Size	Retrospective: 38, 000 Prospective: 13, 684			
Planned Study Period	Funded study period: 1 st Feb	oruary 2021 to 30 th June 2024		
	Prospective sub-study perio	d: 1 st October 2021 to 31 st July	2023	
Planned Recruitment period	Retrospective: 1 st January 19 Prospective: 1 st October 202			
	Objectives	, Outcome Measures	Timepoint(s)	
Primary	Primary Objective To develop and externally validate two prognostic models to predict post- operative atrial fibrillation after cardiac surgery using data available in the pre- operative assessment clinic or on admission for surgery (PARADISE-1) and on arrival in the post- operative care unit (PARADISE-2); and compare their performance to other published models	Primary outcome Discrimination (c-statistic) and calibration (intercept and slope) in external dataset Secondary outcomes Positive and negative predictive values, sensitivity and specificity	7 days after cardiac surgery	
Secondary	 Systematic literature review Analysis of CALIBER database using statistical and machine learning methods 	Candidate risk factors for inclusion in new onset atrial fibrillation prognostic models	For pre-operative model, factors up to surgery, for post-operative model factors up to 12 hours post surgery.	

Clinical Research Protocol Template version 15.0

CONFIDENTIAL

© Copyright: The University of Oxford and Oxford University Hospitals NHS Foundation Trust 2019 Page 8 of 34

development

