7.2.1 Databases

- 1. **CALIBER**: The Health Data Research UK CALIBER research platform contains variables extracted from linked electronic health records from primary care, hospital records, social deprivation information and cause-specific mortality data in England. This dataset includes electronic health records from 6.5 million individuals between 1998 and 2016.
- PRD: The Partners Research Database (PRD) contains detailed modern data for over 30,000 individuals undergoing cardiac surgery from 2 centres in the US between 2001-2020. PRD includes pre-operative echocardiographic measurements.
 Note: During the study, we will expand this database to include pre-and peri-operative variables from the clinical data warehouses of the two centres. It will be used for model development.
- 3. **Brigham**: The Brigham and Women's CABG Genomics Database is a prospective single centre detailed research database comprising 3000 individuals from 2001-2016. This dataset contains over 1,700 prospectively collected and curated pre, intra, and post-operative variables. It will be used for external US retrospective model validation.
- 4. **NHS Trusts**: The study will prospectively collect data from the UK NHS Trusts which will allow us to undertake external validation of PARADISE-1/PARADISE-2 with a total of approximately 6000 patients (2000 AFACS events) per annum. The NHS Trusts where data will be extracted from are:
 - a. Liverpool Heart & Chest NHS Foundation Trust
 - b. Barts Heart Centre (Barts Health NHS Trust)
 - c. Oxford University Hospitals NHS Foundation Trust

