11.3 Sample Size Determination

The model development data set (PRD) contains detailed data for >30,000 individuals undergoing cardiac surgery from 2 centres, 2001-2020. Of these, we expect around one third of patients to have experienced AFACS (10,000 events)

Retrospective external validation on the Brigham data set will comprise 3000 individuals (≈900 AFACS events, much larger than the minimum recommended sample size of 100 events (58).

Data from patients within trials and "real-world" data from patients receiving routine clinical care offer different strengths and weaknesses when validating a prediction rule (59). We will therefore undertake prospective external validations in both trial patients (using data from the ongoing British Heart Foundation (BHF) funded Tight K study CS/18/3/34063 and in a prospective cohort of ≈6000 patients developed from enhanced routine data collection at NHS Trusts.

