### 2.2. OBJECTIVES

To develop and internally validate two prognostic models to predict postoperative atrial fibrillation after cardiac surgery using data available in the pre-operative assessment clinic or at admission for surgery (PARADISE-1); and data available on arrival in the postoperative care unit (PARADISE-2) from a single US centre (Massachusetts General Hospital).

To externally validate the developed models on three separate datasets: a US hospital (Brigham and Women's Hospital), a UK clinical trial (Tight K study) and prospectively collected data from UK NHS cardiac surgery centres.

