#### 3.3.1. Study setting and data collection

We will use the Massachusetts General Hospital (MGH) database to develop the PARADISE prediction models. The MGH dataset has two data sources:

- 1. the Research Patient Data Registry (RPDR): medical record data extracted from electronic hospital systems
- 2. the Society of Thoracic Surgeons (STS) Adult Cardiac Surgery Database: data gathered by trained extractors

Both data sources for the Mass General Hospital dataset will be used to develop our models and we will use retrospective pre-, intra-, and post-operative data for over 10,000 cardiac surgeries performed and recorded at this single US centre between 2003 and 2020.

It is important to note that some tables from this dataset were affected by a change in its electronic medical record system, which changed from Longitudinal Medical Record (LMR) to EPIC in April 2016.

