#### 3.3.2. SAMPLE SIZE CALCULATION

As the two models to be developed are predicting the same outcome (new onset AF in the 7 days after surgery), the same sample size is applicable to both models.

Data on approximately 12,000 surgeries are available from Massachusetts General Hospital between 2003 – 2020 with approximately 20% of patients having new onset AF in the 7 days after surgery.

We used formal sample size formulae for binary outcome measurement provided by Riley et al [28] and the associated 'pmsampsize'[29] sample size calculator in R statistical software programme to calculate the maximum number of candidate predictor parameters we can include during model development. Based on the prevalence and assuming an anticipated R squared between 5% and 15% of the max Cox-Snell R2 (i.e. Cox-Snell R2 between 0.0316 and 0.0948) we can examine up to 42 - 132 predictor parameters for inclusion in the model [28].

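### The protocol and SAP describe different development sets: 30,000 patients with 10,000 events against 10,000–12,000 surgeries with about 1,800–2,400 events, so the protocol's overfitting statement lacks its basis

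*Protocol*

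**What the plan says.** **Protocol.** Section 7.2.1 says the PRD "contains detailed modern data for over 30,000 individuals undergoing cardiac surgery from 2 centres in the US between 2001-2020" and assigns it to model development. Section 7.4 develops both models in it. Section 11.3 repeats the size: "The model development data set (PRD) contains detailed data for >30,000 individuals undergoing cardiac surgery from 2 centres, 2001-2020". Section 11.2.1 draws the conclusion: "we anticipate that around one third of patients will experience AFACS (10,000 events), so the issue of overfitting is negligible". The synopsis gives an overall figure, "Retrospective: 38, 000", without components. This is the protocol's current text. Appendix A runs to version 5 (3 July 2023), and no listed amendment changes the development set.

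**SAP.** Section 2.2 develops and internally validates both models with data "from a single US centre (Massachusetts General Hospital"). Section 3.3.1 describes retrospective data "for over 10,000 cardiac surgeries performed and recorded at this single US centre between 2003 and 2020". Section 3.3.2 says: "Data on approximately 12,000 surgeries are available from Massachusetts General Hospital". The event rate is about 20% in section 3.3.2 and about 18% in section 3.3.4, which adds that 18% informed the sample size calculation. Section 3.3.2 allows 42 to 132 candidate parameters, and section 3.3.4 calls the risk of overfitting low. Section 3.3.3, however, still names the PRD as the source for model development.

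**The concern.** The protocol infers that overfitting is negligible directly from its event count. If the models are developed in the SAP's data, that count is not available and the inference loses its premise. A reader of the protocol would credit the models with between 4.2 times (10,000/2,400) and 5.6 times (10,000/1,800) the events they will have, and with two development centres where the SAP has one.

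The size of the set also decides how long a candidate list it can support. A list that is comfortable under the protocol's figures may miss the usual shrinkage target under the SAP's. Both documents also plan flexible machine learning and a search for interactions, neither of which a simple parameter count fully captures.

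**Working it through.** **1. The protocol's figure.** 30,000 × 1/3 = 10,000 events. It reproduces.

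**2. Events under the SAP's figures.**

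| Surgeries | Rate | Events | Shortfall against 10,000 |
|---|---|---|---|
| 12,000 | 20% | 2,400 | 76% |
| 12,000 | 18% | 2,160 | 78% |
| 10,000 | 20% | 2,000 | 80% |
| 10,000 | 18% | 1,800 | 82% |

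The number of records falls by 60% (12,000 against 30,000) to 67% (10,000 against 30,000). The unit also changes, from individuals to surgeries.

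**3. How much could be the outcome definition?** With incidence kept at the protocol's one third, 12,000 surgeries would give 4,000 events, which is 60% below 10,000. The lower event rate accounts for the rest of the fall, from 4,000 to 2,160–2,400.

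**4. The SAP's parameter range.** The SAP cites the published criteria for a binary-outcome model. It states no target shrinkage; I assume S = 0.90, optimism in R² of at most 0.05 and a margin of 0.05 on overall risk.

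- Maximum Cox-Snell R² at rate φ = 0.20: 1 − exp{2[φ ln φ + (1 − φ) ln(1 − φ)]} = 0.6324. Of this, 5% is 0.0316 and 15% is 0.0949 (SAP: 0.0316 and 0.0948).
- Shrinkage criterion, solved for the number of parameters: P = N(S − 1) ln(1 − R²/S).
- R² = 0.0316: 12,000 × (−0.10) × ln(1 − 0.0316/0.90) = 42.9, so 42 parameters.
- R² = 0.0948: 12,000 × (−0.10) × ln(1 − 0.0948/0.90) = 133.6, so 133 parameters.
- The other two criteria do not bind. The optimism criterion implies S = 0.50 and 0.75 at the two R² values, both less strict than 0.90. The overall-risk criterion needs (1.96/0.05)² × 0.20 × 0.80, about 246 records.

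The SAP states 42 and 132, so its range reproduces at 12,000 and 20%. At 18%, the rate the SAP says it used, the range would be 41–128.

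**5. What the choice of data set does to the cap** (same criteria, R² at 5% and 15% of its maximum):

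| Development set | Parameter range |
|---|---|
| 30,000 at one third | 122–383 |
| 12,000 at 20% | 42–133 |
| 12,000 at 18% | 41–128 |
| 10,000 at 20% | 35–111 |
| 10,000 at 18% | 34–107 |

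**6. Expected shrinkage with 132 parameters.** At 12,000 and 20% it is 0.75 if R² is at the low end and 0.90 at the high end. At 30,000 and one third it would be 0.89 and 0.96.

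**7. The synopsis total.** PRD 30,000 plus Brigham 3,000 (protocol 7.2.1) is 33,000. The remaining 5,000 of the 38,000 is not attributed, and no count of cardiac surgery patients in CALIBER is given.

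**The case against.** The strongest reply is that no analysis step depends on the protocol's statement. Protocol 11.2.1 applies LASSO in the same paragraph. Protocol 11.2.2 plans bootstrap optimism correction, with k-fold cross-validation added for machine learning. SAP 3.5 requires at least 200 bootstrap samples that repeat every modelling step. SAP 3.3.2 makes a formal calculation on the smaller set, and it reproduces. Protocol 11.1 describes its statistics section as a summary of what the SAP will detail. All of this stands. It answers a reader who might infer that overfitting is uncontrolled; the documents do not support that inference.

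The second reply is that the two event counts do not measure the same thing. The protocol counts AF after surgery in all adults having cardiac surgery. The SAP counts new-onset AF, moves prior AF to a sub-analysis (3.2, 3.6) and excludes paced rhythm and several procedure types (3.1.2). That stands in part. Some of the fall in both the rate and the number of records may have this source, and the SAP does not say whether its totals are before or after these exclusions. But an explanation of the fall would not restore the events, and a summary should agree with the plan it summarises.

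**Conclusion.** The inconsistency is real and concerns the development data set, its size, the number of centres and the event rate. On the SAP's figures there are about 1,800 to 2,400 events, 76% to 82% below the protocol's 10,000, and the overfitting statement should not remain on its present basis. The event range rests only on multiplying the SAP's own sizes and rates. The parameter ranges and shrinkage values also rest on the assumed target of 0.90.

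Three stronger readings are not supported:

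- **A calculation error in the protocol.** One third of 30,000 is 10,000; the mismatch is with the SAP.
- **Too few surgeries.** A reader might infer that 12,000 is inadequate. Adequacy depends on the number of candidate parameters, which neither document states (the SAP refers to a Case Report Form), and on where R² falls. With more than 42 parameters the 0.90 target is missed if R² is at the SAP's low end; at the high end there is room up to about 133.
- **A synopsis total built on the 30,000.** That is plausible, but the 38,000 is not broken down, so it remains an inference.

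**What to change.** 1. Name one development data set in both documents. If it is the single hospital, amend protocol 7.2.1, 7.4, 11.2.1 and 11.3, and SAP 3.3.3, which still names the PRD.
2. Give one size, in one unit (patients or surgeries), and one event rate for one stated population, saying whether prior AF and the SAP's exclusions have been removed. Copying the SAP's figures into the protocol as they are would carry over its own conflicts (over 10,000 or about 12,000; 18% or 20%).
3. Restate the event count in the protocol from the agreed figures.
4. Replace the protocol's overfitting statement with the parameter cap, recomputed at the agreed size and rate with its target shrinkage stated, and set the actual number of candidate parameters against it. Bootstrap correction is already in protocol 11.2.2 and need not be added.
5. List the components of the synopsis total of 38,000, and restate it if it includes the 30,000.

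The cost is document wording and less favourable stated numbers. Data collection does not change.
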